The simultaneous administration of drugs that induce microsomal liver enzymes, such as Phenytoin or Phenobarbital, may accelerate the elimination of metronidazole while the simultaneous administration of drugs that decrease microsomal liver enzymes activity, such as ceftrimide, may prolong the half-life and decrease plasma clearance of metronidazole.

Ciprofloxacin may increase the effects of caffeine.

Serious and fatal reactions have occurred when Ciprofloxacin was taken in combination with theophylline. These reactions have included cardiac arrest, seizures, status epilepticus, and respiratory failure.

Tendon disorders (tendinitis) have been rarely encountered in some cases related to concomitant use of quinolone with corticosteroids.

9 Research Question & Study Objectives

9.1 Primary Objective:

9.1.1 Primary Safety:

To compare safety of oral Ciprodiazole[®] tablets (Ciprofolxacin/Metronidazole) versus currently used Ciprofloxacin Tablets & Metronidazole tablets in pelvi-abdominal infections, either non-operative or post-operative following IV antibiotics.

9.1.2 Primary Efficacy:

To compare efficacy of oral Ciprodiazole[®] tablets (Ciprofolxacin/Metronidazole) versus currently used Ciprofloxacin Tablets & Metronidazole tablets in pelvi-abdominal infections, either non-operative or post-operative following IV antibiotics

9.2 Secondary Objective:

9.2.1 Secondary Safety:

- Presence of any signs/symptoms of post-operative wound infection such as redness, fever or wound discharge.
- Presence of undesirable effects on total leukocyte count and liver enzymes (SGOT & SGPT)

9.2.2 Secondary Efficacy:

- To compare the complete resolution or improvement of Pelvi-abdominal infection between ciprodiazole[®] versus combined treatment, based on pelvi-abdominal ultrasound and others
- To compare the days for complete healing of post-operative wounds between ciprodiazole[®] versus combined treatment

10 Research Methods

10.1 Study Design:

This is a single center, open Label, controlled, interventional phase IV Study conducted in Menoufia University Hospital in Egypt to compare the safety and efficacy of oral Ciprodiazole[®] tablets (Ciprofloxacin/Metronidazole) versus currently used Ciprofloxacin Tablets & Metronidazole tablets in pelvi-abdominal infection and following IV antibiotics in post-operative period, for pelvi-abdominal surgeries or acute conditions

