10.5.1 Determination of Sample Size

As the primary objective is to assess the safety of oral Ciprodiazole[®] tablets (Ciprofolxacin /Metronidazole) versus currently used Ciprofloxacin Tablets & Metronidazole tablets following IV antibiotics in post-operative period, for pelvi-abdominal surgeries, and based on the previous study "Comparison of Intravenous/Oral Ciprofloxacin Plus Metronidazole Versus Piperacillin / Tazobactam in the Treatment of Complicated Intra-abdominal Infections".^[15] Overall clinical resolution rates were statistically superior for CIP+MET (74%) compared with PIP/TAZO (63%). Mean length of stay was 14 days for CIP1MET and 17 days for PIP/TAZO patients.

So, the following parameters are used to calculate the expected sample of the study:

- Design: non-inferiority
- Sample Size = 312 Subjects (1:1)
- Ciprodiazole Sample Size (Experimental group) = 156 subjects
- Current used regimen Sample Size (Control group) = 156 subjects
- Confidence level 95% (α error = 5%)
- Power = 80%
- Non-Inferiority margin = 2%

10.5.2 Sample Size & Treatment Groups:

Total of 312 Egyptian patients who have pelvi-abdominal infection or started IV antibiotics in post-operative period, for pelvi-abdominal surgeries will be enrolled in the study and randomized, using a computer system, with a ratio of 1:1, into two categories as follows:

1. Group will receive Ciprodiazole[®] tablets; 156 patients
2. Group will receive Ciprofloxacin Tablets & Metronidazole tablets; 156 patients

10.5.3 Randomization:

Subjects will be randomized into the two treatment groups with a balanced ratio of 1:1. Randomization by block Computer-generated randomization lists will be established by Data Management department (DM) of CRO (Nagy Research). The number of patients of the two treatment groups will be balanced (ratio 1:1). (156 Ciprodiazole[®]: 156 Ciprofloxacin Tablets & Metronidazole tablets).

A document describing the procedure of constitution of the randomization lists will be stored confidentially at Nagy Research CRO

Block size: 2, 4

The Randomization list will be done using website:
(<https://www.sealedenvelope.com/simple-randomiser/v1/lists>)

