10.7.3 Analysis variables

Descriptive Analysis:

- Descriptive analysis of the collected data. All enrolled patients will be included in the safety analysis.
- All quantitative primary and secondary end point variables will be described
- Data from primary and secondary endpoints will be summarized using appropriate summary statistics i.e. n (number of subjects), mean, Standard Deviation (SD), median and range.

Comparative Analysis:

- All tests will be performed on the 5% level of significance.
- Chi² test for unpaired categorical variables.
- Paired t-test to estimate the change in numerical variables throughout the study visits.
- Student t-test to estimate the comparison between the subgroups for the numerical variables.
- *P*-values less than 0.05 will be considered statistically significant

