9.4 Primary End Point

9.4.1 Primary Safety

Table 4 *Number and percent of Adverse Event necessitating a change or discontinuation of treatment among treatment groups*

	Group A (N=156)	Group B (N=156)	p-value
Total No of SAE, N (%)			
SAE1, N (%)			
SAE2, N (%)			
SAE3, N (%)			

Table 5 *Number and percent of Serious Adverse Event among treatment groups*

	Group A (N=156)	Group B (N=156)	p-value
Total No of SAE, N (%)			
SAE1, N (%)			
SAE2, N (%)			
SAE3, N (%)			

Table 6 *Number and percent of causes of treatment discontinuations among treatment groups*

	Group A (N=156)	Group B (N=156)	p-value
Total No of treatment discontinuations, N (%)			
Cause1, N (%)			
Cause2, N (%)			
Cause3, N (%)			

Table 7 *Number and percent of Adverse Event necessitating a change or discontinuation of treatment among treatment groups*

	Group A (N=156)	Group B (N=156)	p-value
Total No of AE, N (%)			
AE1, N (%)			
AE2, N (%)			
AE3, N (%)			

Table 8 *Number and percent of Adverse Event among treatment groups*

	Group A (N=156)	Group B (N=156)	p-value
Total No of AE, N (%)			
AE1, N (%)			
AE2, N (%)			
AE3, N (%)			

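### AE and SAE incidence is compared by pooled, unadjusted chi-square with no stated stratification by operative status, so the plan gives up a little precision and has no AE/SAE result for either entry group

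*Protocol*

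**What the plan says.** **Population.** The primary safety objective (Protocol 9.1.1 and 10.7.4, SAP 1.1.1 and 8.4) compares the regimens in patients "either non-operative or post-operative following IV antibiotics". The sample-size text (Protocol 10.5.1, SAP 7.1) describes the safety objective for the post-operative setting only. Protocol 10.1 and SAP 2 join the two routes of entry with and/or, so a patient may belong to both.

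**Randomisation.** Protocol 10.5.3 and SAP 7.3 state "Subjects will be randomized into the two treatment groups with a balanced ratio of 1:1", with blocks of 2 and 4 and planned totals of 156:156. No stratification factor is named. Both sections speak of lists in the plural and refer to a procedure document held at the CRO, which is not among the files.

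**Analysis.** Safety is analysed in all treated patients together (Protocol 10.7.1, SAP 8.1). The general rule is "Chi² test for unpaired categorical variables", and Protocol 10.7.6 and SAP 8.6 apply it to every primary safety item without adjustment.

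**Tables.** SAP Tables 4-8, for example Table 5 ("Number and percent of Serious Adverse Event among treatment groups"), have one column per arm headed N=156 and a p-value. None has a row or column for entry group.

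**The concern.** The protocol itself gives reasons to expect different background event rates in the two groups:

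- Its introduction places the peak of post-operative complications at one to three days after surgery. Post-operative patients move to oral treatment after 48 hours of IV antibiotics, or once they tolerate oral intake, so AE collection can overlap that peak.
- A prolonged hospital stay counts as an SAE (Protocol 13.2), which depends on being an inpatient.
- Cholecystitis that goes to surgery is a reason for withdrawal (Protocol 10.2.3). It concerns the infection group and would feed Table 6.

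Operative status is therefore a plausible prognostic factor, available before allocation at no cost. Leaving it out of the analysis leaves its variation in the error term. Leaving it out of the tables means that an excess of events in one group could be diluted by the other with no planned output to show it, although the primary objective names both groups.

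**Working it through.** **1. The plan's own figure.** The 312 comes from resolution rates of 63% (control) and 74% (experimental), a 2-point margin, 80% power and a 5% error rate taken as one-sided:

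n per arm = (1.645 + 0.842)² × (0.63×0.37 + 0.74×0.26) / (0.74 − 0.63 + 0.02)² = 6.183 × 0.4255 / 0.0169 = 155.7, so 156 per arm and 312 in total.

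The figure reproduces. The rates are clinical resolution rates from a cited trial; no AE rate enters.

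**2. Assumed inputs.** The documents give neither the post-operative share *s* nor the outcome gap *g* between entry groups. I take *s* = 50% (which maximises the imbalance) and *g* = 10, 20 or 30 points.

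**3. Chance imbalance.** SD of the between-arm difference in post-operative share = √(s(1−s) × 2/156) = √(0.25 × 2/156) = 5.7 points, so the 95% range is ±11.1 points, or about 17 of 156 patients. The resulting shift in the pooled difference is *g* × imbalance: ±1.1, 2.2 or 3.3 points. At *s* = 20% it is ±0.9, 1.8 or 2.7 points.

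**4. Validity.** This shift is one component of the unadjusted standard error, which is √(2×0.74×0.26/156) = 5.0 points at a 74% rate. In simulated trials with blocks of 2 and 4 from one unstratified list (12,000 per gap), two-sided type I error was 4.8-4.9% for the plain chi-square and 4.8-4.9% for the stratified Cochran-Mantel-Haenszel test.

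**5. Precision gained by adjusting.** Share of variance removed = s(1−s)g² / [p(1−p)], with *p* the mean rate and *s* = 50%:

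| Gap | p = 74%: variance cut | 95% half-width (9.7 unadjusted) | p = 20%: variance cut | 95% half-width (8.9 unadjusted) |
|---|---|---|---|---|
| 10 points | 1.3% | 9.7 | 1.6% | 8.8 |
| 20 points | 5.2% | 9.5 | 6.3% | 8.6 |
| 30 points | 11.7% | 9.1 | 14.1% | 8.2 |

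For example, 0.25 × 0.20² / 0.1924 = 5.2%. The 20% column is an assumed AE rate.

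**6. Rare events.** Rarity limits the gap. At an assumed 5% overall SAE rate and *s* = 50%, the largest possible gap is 10 points (0% v 10%), so the cut cannot exceed 0.25 × 0.10² / (0.05×0.95) = 5.3%. With one group at twice the rate of the other, the gap is 13.3 points at a 20% mean (13.3% v 26.7%) and the cut is 0.25 × 0.133² / 0.16 = 2.8%. At a 5% mean the gap is 3.3 points (3.3% v 6.7%) and the cut is 0.25 × 0.033² / 0.0475 = 0.6%.

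**7. Precision within an entry group.** At an assumed 20% AE rate with 78 per arm, half-width = 1.96 × √(2×0.2×0.8/78) = 12.6 points. With about 31 per arm (*s* = 20%) it is 19.8 points. Pooled, it is 8.9 points.

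**The case against.** The best case against is that this is largely a design preference. The unstratified chi-square is valid, the precision gain is modest under most assumptions, and subgroup rows will be too imprecise to settle anything. The wording of the objective can also be read as describing who is eligible, not as promising two estimates. The silence on stratification is not proof of its absence, because the CRO's document may provide it. All of this stands, and it limits the point to an inexpensive improvement. It does not remove it: if the lists are stratified, the protocol should say so and the analysis should use the factor; if they are not, a known baseline variable goes unused.

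Two stronger readings are tempting and are not supported.

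- A reader might infer that chance imbalance can move the safety result by as much as the margin. The line "Non-Inferiority margin = 2" (per cent) names no endpoint, sits beside efficacy rates, and is used in no planned test. A shift of that size also depends on an assumed gap: at *s* = 50% its chance is 0.04%, 7.7% or 24% for gaps of 10, 20 or 30 points. Above all, it is random error already counted in the standard error, not bias.
- A reader might infer that neither group gets any safety answer. A pooled answer is planned for all treated patients, and signs of post-operative wound infection are tabulated in SAP Table 11. What is missing is an AE/SAE result by entry group.

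Nor does the point extend to the primary efficacy tests as a pooling fault. Infection resolution and wound healing are tested separately (Protocol 10.7.7, SAP 8.7).

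**Conclusion.** The point holds as a low-cost improvement. No stratification factor is stated, the primary AE/SAE comparisons are pooled and unadjusted, and no AE/SAE result by entry group is planned although the primary objective names both groups. The comparison stays unbiased and its type I error stays at the nominal level.

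The loss is one of precision and reporting. Under an assumed 50% post-operative share and a 74% mean rate, the variance reduction forgone is about 1%, 5% or 12% for assumed gaps of 10, 20 or 30 points. It is of similar order at an assumed 20% AE rate, and small for rare events such as SAEs, where large gaps cannot occur. The share and the gap are assumptions, because the documents give neither. The reporting gap does not depend on them. Stratification would not alter the assumptions behind the 312.

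**What to change.** 1. **Protocol 10.5.3 and SAP 7.3.** Stratify the randomisation list by operative status at entry (post-operative: yes or no). State that a patient with both infection and recent surgery counts as post-operative, since the and/or wording in Protocol 10.1 and SAP 2 allows both. If the CRO's procedure already stratifies, state the factor here.
2. **Protocol 10.7.6 and SAP 8.6.** Report AE and SAE incidence as a Mantel-Haenszel risk difference with a 95% confidence interval, stratified by that factor.
3. **SAP Tables 4-8.** Add a row for each entry group with its own denominator. Label these rows descriptive and give them no p-values.

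If enrolment has begun, leave the randomisation alone and adopt items 2 and 3 only. Protocol 10.7.2 and SAP 8.2 provide for a final SAP before database lock in which differences are documented.

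**Cost.** One more item must be recorded before allocation, and the SAP edit is short. Arm totals may depart slightly from 156:156: each of two lists can end in an incomplete block of 4 with an imbalance of at most 2, so the totals could differ by up to 4 (158:154). The entry-group rows will be imprecise, about ±12.6 points with 78 per arm at an assumed 20% AE rate, and should be read that way.

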10.6 Data Management

Data will be entered into a computer database with independent double data entry and will be validated with computer checks and manual review against source files. The patient's data will remain confidential, since only the patients' initials are on the CRFs. Queries will be sent to the investigators using data clarification forms, and resolved by the investigators who will sign and date the respective data clarification forms. Corresponding changes in the database will be made, documented, and independently verified. Subjects who drop out will fill the reason for premature end of the study and will be documented.

10.7 Data Analysis

10.7.1 Analysis populations

Analysis of all efficacy variables will be performed only for patients who completed the study without protocol violation (as per protocol).

Analysis of all safety variables will be performed for all patients (intent-to-treat population), who received even 1 dose of the treatment; either Ciprodiazole[®] tablets or currently used Ciprofloxacin Tablets & Metronidazole tablets.

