4. Subjects who are willing to sign Informed Consent Form (ICF) and ready to comply with the protocol for the duration of the study

10.2.2 Exclusion Criteria:

Subjects presenting with any of the following will not be included in the study:

1. Subjects with a history of hypersensitivity to any of the active ingredients of the treatments used
2. Subjects who are receiving or received any other antibiotics during the previous two weeks, rather than IV treatment in the first post-operative 48 hours, mentioned in the protocol (Metronidazole injection plus third generation cephalosporin)
3. Subjects with Pelvi-abdominal infection and performed surgery after failure of oral antibiotics.
4. Subjects having surgeries such as colorectal surgeries, appendectomy and ovarian cystectomy
5. Subjects with any medical condition requiring the usage of the following medications:

- a. Drugs that induce microsomal liver enzymes, such as Phenytoin or Phenobarbital, may accelerate the elimination of metronidazole
 - b. Drugs that decrease microsomal liver enzymes activity, such as cefrimide, may prolong the half-life and decrease plasma clearance of metronidazole.
 - c. Administration of theophylline in combination with Ciprofloxacin may lead to cardiac arrest, seizures, status epilepticus, and respiratory failure
 - d. Administration of corticosteroids in combination with Ciprofloxacin may lead to tendinitis
 - e. Antacids containing magnesium and aluminum, supplements and other products containing calcium, iron or zinc as they reduce the effect of Ciprofloxacin.
 - f. Tizanidine because this may cause low blood pressure and sleepiness
6. Subjects with uncontrolled diabetes mellitus; FBG > 200 mg/ml
 7. Subjects with renal impairment (S. Creatinine > 1.5 mg/dL)
 8. Subjects with hepatic impairment (Child-Pugh Score B-C)
 9. Subjects with liver enzymes (SGOT, SGPT) > 2 times Normal range.
 10. Pregnant or breast feeding women

10.2.3 Discontinuation/Withdrawal of participants from the study:

Each participant has the right to withdraw from the study at any time.

In addition, the investigator may discontinue a participant from the study at any time if the investigator considers it necessary for any reason including:

1. Ineligibility (either arising during the study or retrospective having been overlooked at screening)
2. Significant protocol deviation
3. Significant non-compliance with treatment regimen or study requirements

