4. Disease progressions which requires discontinuation of the study medication or results in inability to continue to comply with study procedures.
5. Consent withdrawn by subject.
6. Lost to follow up
7. SAE or death
8. If a female subject becomes pregnant
9. Subjects which have Cholecystitis and it will be operated upon.

The reason for withdrawal will be recorded in the CRF. If the participant is withdrawn due to an adverse event, the investigator will arrange for follow-up visits or telephone calls until the adverse event has resolved or stabilized.

10.2.4 Assessments to be done:

1- Screening Visit Assessments:

- The enrollment period will be 12 months including the screening visit. Screening assessments will be completed and treatment will be initiated within visit 1.
- During this visit, patients will be screened for fulfillment of the inclusion and exclusion criteria and written informed consent will be obtained.
- Screening assessments will include physical examination, medical history, patient demographics, vital signs, concomitant medications, safety laboratory tests

(including Fasting Blood Sugar (FBS), Total leukocyte count, Liver enzymes (SGOT & SGPT), Total Bilirubin and S. Creatinine), Child-Pugh Score (for hepatic impairment) and, β -HCG (for females of child bearing potential only) and pelvi-abdominal Ultrasound & others.

- Presence of any signs/symptoms of post-operative wound infection such as redness, fever or wound discharge will be recorded (in case of post-operative subjects)

2- Follow-up 1 Visit:(Day 8):

- On-treatment assessments include physical examination, vital signs, AEs, SAEs, concomitant medication and study drug dosing compliance
- Days for complete healing will be checked
- Complete resolution, improvement, failure or relapse of Pelvi- abdominal infection
- Presence of any signs/symptoms of post-operative wound infection such as redness, fever or wound discharge will be recorded (in case of post-operative subjects)

3- Follow-up 2 Visit & End of study visit (Day 15):

- Assessments include physical examination for vital signs, AEs, SAEs, concomitant medication, and study drug dosing compliance
- Pelvi-abdominal Ultrasound and others will be done, if needed upon Physician's decision.
- Days for complete healing will be checked
- Complete resolution, improvement, failure or relapse of Pelvi- abdominal infection

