12.2 Patient Enrollment

After signing the informed consent form, each potential subject will be screened for eligibility based on the inclusion and exclusion criteria specified. Randomization will be done.

All visits will occur as closely as possible to the scheduled visit dates with window of 3 days. In case of a premature discontinuation of the study, the subject, will be, if possible called in for a last visit. Even if the subject would not be able to attend, the 'End of Study' forms will be completed .

12.3 12.3 Schedule of visits

Table 1: Schedule of Visits

Observation	Visit 1 (Screening & treatment)	(Follow-up 1 V)	(Follow-up 2 V) End of Study
Time lines	Day 0	Day 8	Day 15
Informed consent document signed	X		
Review Inclusion/Exclusion criteria	X		
Patient Demographics	X		
Significant medical history and current disease status	X		
Physical examination	X	X	X
Vital Signs	X	X	X
Child-Pugh Score	X		
Concomitant medications	X	X	X
Safety Laboratory Tests:			
FBS	X		
Total Leucocytic count	X		X
SGOT (ALT)	X		X
SGPT (AST)	X		X
Total Bilirubin	X		X
S. Creatinine	X		X
Serum β -HCG: (for females in childbearing period)	X		
Pelvi-abdominal Ultrasound & others (Optional)	X		X
Study Drug Dispensed	X	X	
Drug Accountability		X	X

Observation	Visit 1 (Screening & treatment)	(Follow-up 1 V)	(Follow-up 2 V) End of Study
Time lines	Day 0	Day 8	Day 15
Presence of any signs/symptoms of post-operative wound infection such as redness, fever or wound discharge. (in case of post-operative subjects)	X	X	X
Days for complete healing		X	X
Complete resolution, improvement, failure or relapse of pelvi - abdominal infection		X	X
AE		X	X
SAE		X	X
Study Completion Form			X

The subsequent visits will occur as follows :

- **Visit 1 (Screening & treatment initiation Visit):** Day 0
- **Follow-up V1:** Day 8 (+/-) 3 days
- **Follow-up V2 & End of Study Visit:** Day 15 (+/-) 3 days

12.3.1 Visit 1 (Screening & treatment initiation):

- During this visit, subjects will be informed about the study. If they are willing to participate in the study, they will sign the written ICF. A copy of the signed ICF will be given to the subject. In addition, the subjects will be evaluated for study eligibility according to the inclusion and exclusion criteria.
- Screening Assessments will include: physical examination, vital signs, demographic data (Age & Gender), medical history and concomitant medications.

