14.2 Final Study Report

The final study report will be submitted as soon as possible within 3 months of database lock. If the study is discontinued for any reason; a final report will be submitted and the reasons for terminating will be provided. The title, version and date of the protocol and author will be written in the title page.

The final study report will follow Arab GVP content & include but not limited to:

An abstract of the study, rationale and background, research methods, demographic, baseline characteristics, safety parameters will be analyzed for the total population of all enrolled (randomized) subjects. Efficacy analysis will be performed for the 'Per Protocol populations only. ITT patients will be analyzed for safety in the results section; results and limitations will be discussed in the discussion section of the report.

Population is defined as follows :

- Intention to Treat (ITT): all enrolled subjects with at least one baseline and one post-baseline visit.
- Per Protocol (PP): all enrolled subjects who completed according to the protocol with no protocol deviations.

Continuous variables will be summarized using mean, standard deviation, median, and range (minimum and maximum), while categorical variables will be summarized using proportions (counts and percentages) .

Data on subject disposition (number of subjects enrolled, number of drop-outs, and reasons for drop-out), demographics (gender, age, weight, height), and other baseline characteristics (physical examination results, vital signs, and laboratory assessments) will be summarized.

All biostatistical results and analysis will be done as per endpoints as per protocol, as per section 10.7.

Additionally, for each treatment, the incidences of all treatment emergent AEs will be tabulated by body system and preferred term (to which each AE will be mapped, using World Health Organization Adverse Reaction Terminology (WHO-ART), version 1998/04). Other information regarding AEs, such as intensity, seriousness, causality, and discontinuations due to AEs, will be also tabulated by treatment. AEs that are reported

more than once by a subject will be counted only once for that subject at the maximum intensity.

Concomitant medications will be tabulated by generic drug names, based on World Health Organization Drug Dictionary (WHO-DD), version 1998/04.

15 Confidentiality and publication

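### Efficacy is analysed only in completers without protocol violation, so failures whom the unblinded investigator withdraws drop out of both primary efficacy endpoints

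*Protocol*

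**What the plan says.** Protocol 10.7.1 limits efficacy as follows: "Analysis of all efficacy variables will be performed only for patients who completed the study without protocol violation (as per protocol". SAP 8.1 carries the same sentence. Protocol 14.2 again confines efficacy to the per-protocol set, reserves intention-to-treat for safety, and defines the set strictly: "Per Protocol (PP): all enrolled subjects who completed according to the protocol with no protocol deviations". It draws no line between major and minor deviations.

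The trial is open label. Under Protocol 10.2.3, "the investigator may discontinue a participant from the study at any time if the investigator considers it necessary for any reason including" a list that contains "Disease progressions which requires discontinuation of the study medication or results in inability to continue to comply with study procedures", a serious adverse event or death, and "Subjects which have Cholecystitis and it will be operated upon".

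Protocol 12.2 adds: "In case of a premature discontinuation of the study, the subject, will be, if possible called in for a last visit". Protocol 12.3.2 lets a patient with complete resolution at Day 8 finish the study then, with end-of-study laboratory tests and form. It has no matching rule that keeps an early failure in the analysis.

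The planned test for both primary efficacy endpoints is chi-square (Protocol 10.7.3 and 10.7.7: "Chi² test for unpaired categorical variables"). Protocol 10.5.1 names a non-inferiority design with a 2% margin. SAP Tables 9, 10 and 15 are headed with 156 per group, the full randomised number.

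Safety populations: Protocol 10.7.1 and SAP 8.1 require at least one dose. Protocol 10.7.3 says "All enrolled patients will be included in the safety analysis". Protocol 14.2 defines intention-to-treat by a baseline visit and a post-baseline visit.

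**The concern.** Progression, and surgery or death from the infection, are close to the opposite of complete resolution. A patient who fails but stays to Day 15 without a deviation is counted as a failure. One who fails and is withdrawn leaves both numerator and denominator. A last visit does not bring that patient back, because on the natural reading the patient did not complete.

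If similar shares of failures are withdrawn in the two arms, both success rates are inflated and a real deficit shrinks towards zero. If the shares differ, the comparison can move either way, and identical treatments can look different. Unequal shares are plausible. The decision is unblinded, and significant non-compliance is also a withdrawal reason while the arms have different tablet schedules (Protocol 8.4). A non-inferiority conclusion would have the same weakness.

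**Working it through.** **The plan's own figure.** 156 per arm reproduces with 63% control, 74% experimental, a 2-point margin, 80% power and one-sided 5%. The roles of the two rates and the sidedness are inferred, because this combination gives the stated number:

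n = (1.645 + 0.842)² × (0.63×0.37 + 0.74×0.26) / (0.11 + 0.02)² = 6.18 × 0.4255 / 0.0169 ≈ 156.

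It contains no allowance for exclusions. On those same inputs, power is 80.1% at 156 evaluable per arm, 76.2% at 140 and 72.0% at 125.

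**Inputs for the bias.** 156 per arm, all evaluable for the endpoint (assumed). Control success 74%, the rate that Protocol 10.5.1 quotes for ciprofloxacin plus metronidazole, which is this trial's control regimen. The share f of an arm's failures that is withdrawn is assumed; successes are all retained.

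**Formulas.**
- Per-protocol rate = p / [p + (1−p)(1−f)]
- Evaluable number = 156 × [p + (1−p)(1−f)]
- Chi-square: pooled standard error under the null, two-sided 5%
- Non-inferiority: unpooled standard error, one-sided 5%, margin 2 points

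**Identical arms, 74% in each, f = 25% and 50%.**
- Failures withdrawn: 156 × 0.26 × 0.25 ≈ 10 and 156 × 0.26 × 0.50 ≈ 20.
- Rates: 0.74/0.935 = 79.1% and 0.74/0.87 = 85.1%, on 145.9 and 135.7 patients. Spurious difference 5.9 points.
- Standard errors 0.0458 (pooled) and 0.0455 (unpooled). Rejection ≈ 1 − Φ[(1.96×0.0458 − 0.0591)/0.0455] = 1 − Φ(0.67) ≈ 25%. A simulation of 400,000 trials gave 25.1%.
- The arm that withdraws more of its failures is the one favoured.

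**All scenarios** (f given as control/new):

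| True control v new | f | Per-protocol difference (new − control) | Result |
|---|---|---|---|
| 74 v 74 | 25%/50% | +5.9 points | chi-square rejects 25% |
| 74 v 74 | 25%/35% | +2.3 | rejects 7.7% |
| 74 v 64 | none | −10.0 | power 48% |
| 74 v 64 | 50%/50% | −7.0 | power 31% |
| 74 v 64 | 25%/50% | −1.1 | power about 6% |
| 74 v 64 | 50%/25% | −14.7 | power 84% |
| 74 v 72 | none | −2.0 | false non-inferiority 5.0% |
| 74 v 72 | 50%/50% | −1.3 | about 7% |
| 74 v 72 | 25%/35% | +0.7 | 14% |
| 74 v 72 | 25%/50% | +4.6 | 41% |
| 74 v 72 | 50%/25% | −7.6 | 0.2% |

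At a true 10-point deficit with 25%/50%, the lower bound is typically −1.1 − 1.645×4.97 ≈ −9.3 points. Non-inferiority is then declared only about 7% of the time, so the bias does not by itself hand a clearly worse treatment a pass.

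**How few patients matter.** At 74% of 156 (115.4 successes), dropping 4 failures from one arm gives 115.4/152 = 75.9%, a shift of 1.95 points. Dropping 5 gives 2.45 points. Four to five patients are worth about the whole margin.

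**The case against.** - **Per-protocol is normal for non-inferiority, and failures seen at Days 8 and 15 are recorded.** Both are true. The defect is that per-protocol is the only efficacy analysis and that withdrawn failures are lost from it.
- **156 per arm is too many.** Patients enter with an infection or after surgery, so neither endpoint may apply to everyone. This stands against the error rates. With an assumed 78 per arm, the 25% false-positive rate becomes about 15%, the 7.7% becomes 6.3%, and the 41% false non-inferiority becomes 26%. The bias in points is unchanged.
- **74% is a resolution rate; no healing rate is given.** This stands. With assumed healing of 90% or 95%, shares of 25% and 50% give 2.4 or 1.2 points and 13.6% or 9.4% false positives at 156 per arm.
- **The withdrawal shares are invented, and twofold imbalance is severe.** They are assumptions. The milder rows show smaller effects.
- **The one-sided 5% bound is inferred.** At one-sided 2.5%, 41% becomes 29%.
- **A serious adverse event is not necessarily an efficacy failure, an operation for cholecystitis may have been planned, and death is not discretionary.** All correct, and a reason to define which withdrawals count as failures. All of these patients still leave the efficacy set.
- **The 156 header is on every SAP shell and looks like a placeholder, and drop-outs with reasons are already summarised (Protocol 14.2, SAP Table 6).** Fair. The denominator still needs stating, and exclusions for deviations are not tabulated.

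**Conclusion.** The concern holds and must be fixed. Three sections in two documents make per-protocol the sole efficacy analysis, and none retains a patient withdrawn because treatment failed. The direction and size of the bias cannot be fixed in advance, because no withdrawal rate is given. For identical arms under the assumed shares, the false-positive rate runs from 7.7% to 25% at 156 per arm and from 6.3% to about 15% at 78. A true 10-point deficit can appear as anything from 1.1 to 14.7 points. These sizes rest on the assumed shares, the 74% rate and the evaluable numbers; the mechanism does not.

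The three wordings of the safety set are a smaller, separate inconsistency. The one in Protocol 14.2 could drop a treated patient who dies or leaves before any follow-up visit.

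**What to change.** In Protocol 10.7.1 and 14.2 and SAP 8.1:

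1. Add an efficacy analysis of all randomised patients to whom the endpoint applies. Count withdrawal for progression, surgery for the infection, another antibiotic for the infection, or death as not resolved or not healed.
2. Pre-specify a rule for other withdrawals (including other serious adverse events) and missing outcomes, with sensitivity analyses that include best and worst cases by arm. Do not rely on missing-as-failure alone, since it also shrinks differences: with 20% uninformative missingness in each arm, a 10-point difference becomes 0.8 × 10 = 8.
3. Keep the per-protocol analysis, and require both analyses to support any non-inferiority conclusion.
4. In SAP Tables 9, 10 and 15 (and 16 and 17, which share the header), replace 156 with the number analysed in each set. Tabulate exclusions by arm and reason.
5. Use one safety set throughout (at least one dose, as in Protocol 10.7.1 and SAP 8.1), and delete the post-baseline-visit condition in Protocol 14.2.

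The cost is wording and one more analysis. The CRF already records withdrawal reasons, a last visit is already sought where possible, and Protocol 10.7.2 provides for a final SAP before database lock. Reported success rates will be lower, and the rule for other missing outcomes needs a decision because no single rule is neutral.
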